A repeated measures ANOVA analysis will be used to compare changes in intuitive eating, diet quality and food agency over time both within the groups and between the groups. A generalized linear mixed model design will be used to compare the frequency of cooking at home each week over time and between the groups.

Aim 2: To evaluate if providing students with six weeks of a meal delivery service and then six weeks of recipes after completion of cooking classes maintains gains in diet quality, cooking frequency, intuitive eating, and food agency.

Hypothesis 2a: Meal delivery service will better maintain cooking frequency, intuitive eating skills, food agency and diet quality versus recipe provision only. Both meal delivery service and recipe provision will result in more frequent cooking, higher food agency, and higher diet quality the provision of no cooking support.

Hypothesis 2b: During both meal delivery service provision and recipe provision, those in the Cooking Class Condition will maintain higher levels of food agency, cooking frequency, and diet quality than those in the Control Condition.

Repeated measures ANOVA analyses will be used to compare between subjects effects from the meal delivery and recipe only interventions, as well as to compare the material support interventions against the control group. Repeated measures ANOVA will also be used to compare within subjects effects from end of fall semester to the end of each six-week material support intervention.

Aim 3: To positively influence participants' stress levels.

Hypothesis 3: Participants receiving cooking support will have lower scores on a measure of perceived stress than participants who do not receive cooking support. This will be true at all measurement time points.

A repeated measures ANOVA will be used to determine differences both between groups and over time in scores of perceived stress.

Aim 4: To explore the reasons why students cook or do not cook.

Hypothesis 4: There will be common themes defining why student choose to cook or not cook at home.

This is an exploratory aim, and qualitative analysis will be used to deduce popular themes.

Sample Size

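### Repeated measures ANOVA with no rule for missed assessments can discard observed follow-up in Aims 2 and 3, and the planned tests are not the phase-specific ones that Hypotheses 2a, 2b and 3 need

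*Combined protocol and SAP*

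**What the plan says.** All the analysis text is under Statistical Considerations. For Aim 1: "A repeated measures ANOVA analysis will be used to compare changes in intuitive eating, diet quality and food agency over time both within the groups". For Aim 2: "Repeated measures ANOVA analyses will be used to compare between subjects effects from the meal delivery and recipe only interventions", and the same method is to "compare within subjects effects from end of fall semester to the end of each six-week material support intervention". For Aim 3: "A repeated measures ANOVA will be used to determine differences both between groups and over time in scores of perceived stress". Only cooking frequency is treated differently: "A generalized linear mixed model design will be used to compare the frequency of cooking at home each week over time and between the groups".

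The hypotheses are specific about time. Hypothesis 2a says "Meal delivery service will better maintain cooking frequency, intuitive eating skills, food agency and diet quality versus recipe provision only", and adds that both forms of support will beat none. Hypothesis 2b says that, during both support phases, "those in the Cooking Class Condition will maintain higher levels of food agency, cooking frequency, and diet quality than those in the Control Condition". Hypothesis 3 says of lower stress: "This will be true at all measurement time points".

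No section gives an analysis set or a rule for a missed assessment. Three passages come near, but none is an analysis rule:
- Inclusion/Exclusion Criteria makes baseline completion a condition of entry.
- Direct Data Entry by Participants checks items within a form that is being submitted.
- Withdrawal Procedures lets students leave at any time.

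Survey timing is stated inconsistently. The paragraph before Table 1 in Procedures has surveys at baseline and study end only. The later text on questionnaire administration has them at baseline and after each phase, and the Perceived Stress Scale entry says every six weeks. Table 1 lost most of its marks in the text used here, so it is not relied on.

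**The concern.** There are two separate problems.

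The first is lost data. Classical repeated measures ANOVA needs a complete row for each student. Baseline is complete by eligibility, so gaps arise at the three follow-ups. A model covering all of them deletes a student's observed Phase 1 and Phase 2 scores if only Phase 3 is missing. Phase 3 follows a six-week Phase 2 that began in mid-January 2020, and a COVID-19 questionnaire on changed living situations was added, so loss could plausibly concentrate there. The Sample Size section claims no power but says that these data will size a larger study. Needlessly imprecise estimates, or biased ones if loss depends on earlier scores, would pass into that calculation.

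The second is the match between test and hypothesis, and it holds even with complete data. No contrast at a given phase is written for Hypotheses 2a, 2b or 3.

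**Working it through.** **Inputs from the documents.** Four groups of 16 give 4 × 16 = 64, which reproduces the stated sample size; it is lab-capacity arithmetic, not a power calculation. There is a baseline and three follow-ups, if the end-of-phase schedule is the operative one.

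**Assumed, because the documents give no figure.** Loss of 10% or 20% per follow-up, within-person correlation 0.5, SD 1, and a contrast of two groups against two (32 v 32).

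**Students kept by a model using all three follow-ups.** 64 × 0.9³ = 46.7 and 64 × 0.8³ = 32.8. At any single follow-up, 64 × 0.9 = 57.6 and 64 × 0.8 = 51.2 are observed. Follow-up records collected number 3 × 57.6 = 172.8 and 3 × 51.2 = 153.6. Those kept number 3 × 46.7 = 140.0 and 3 × 32.8 = 98.3, so 19% and 36% of collected records are discarded.

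**Standard errors.** A change score has variance 2(1 − 0.5) = 1, so with n students in two equal halves SE = √(4/n). Complete-case: √(4/46.7) = 0.293 and √(4/32.8) = 0.349. The mixed-model SE is √(c′I⁻¹c), where I sums each missingness pattern's information. Averaged over 600 missingness draws, in SD units:

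| Contrast and loss pattern | Complete-case | Mixed model |
|---|---|---|
| Change from baseline at Phase 2, independent loss 10% / 20% | 0.294 / 0.354 | 0.259 / 0.270 |
| Same, permanent dropout 10% / 20% per phase | 0.295 / 0.356 | 0.271 / 0.298 |
| Change from baseline at Phase 3, same dropout | 0.295 / 0.356 | 0.281 / 0.325 |
| Change from baseline at Phase 2, loss only at Phase 3, 20% / 40% | 0.280 / 0.326 | 0.250 / 0.250 |

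**Aim 2 fitted as pairs.** Both end of fall and Phase 2 are observed for 64 × 0.9² = 51.8 and 64 × 0.8² = 41.0 students, so SE = √(4/51.8) = 0.278 and √(4/41.0) = 0.312. The averaged values are 0.278 / 0.315, against 0.267 / 0.288 for the mixed model.

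**Aim 1 with two levels.** For an assumed 0.7 SD effect, power is 74% v 75% at 10% loss and 69% v 72% at 20%.

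**Bias.** In one simulated case (true effect 0, about 16% dropout, unsupported students with low Phase 1 scores leaving), the Phase 2 estimate was −0.12 SD for complete cases and 0.02 SD for the mixed model, each with Monte Carlo SE 0.02.

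**What the planned tests can show.**
- A time-averaged main effect can be significant when the effect is absent in one phase. Take class v control, a fixed 32 v 32 split, with a 0.9 SD effect at Phases 1 and 2 and none at Phase 3. Over four levels it averages (0 + 0.9 + 0.9 + 0)/4 = 0.45, with SE √(2 × 0.625/32) = 0.198. That is significant about 61% of the time on 62 df, although the Phase 3 part of Hypothesis 2b is then false.
- A group-by-time test shows that groups change differently, but not at which phase. If the Aim 2 levels start at the end of fall, a class advantage that is fully maintained produces no interaction at all.
- For stress, no fixed split separates supported from unsupported students. Those in receipt are A+B in Phase 1 and A+C in Phases 2 and 3, and at baseline nobody is.

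**The case against.** The strongest reply is that the loss depends on a model the plan does not fix. The Aim 2 wording can be read as separate pairs, in which case a student missing only Phase 3 stays in the Phase 2 comparison. That stands, and it removes most of the loss. Simply using all available data per phase gives 0.264 / 0.280 for change from baseline under independent loss, close to the mixed model, and equals it at Phase 2 (0.250) when only Phase 3 is lost. The plan does not commit to that reading, however, and Aim 3 is worded across all time points.

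It is also fair that the Aim 1 analysis gains almost nothing, and that the plan does compare change between groups. A reader might infer that the plan offers only a time-averaged main effect; its own wording shows otherwise. The gap is that no contrast at a given phase follows from either test.

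A reader might also infer that a third to a half of the sample will be lost, or that COVID-19 caused heavy Phase 3 loss. The documents give no loss figure, and they describe retention measures: baseline tasks, reminders, incentives, a helpline and paper forms.

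Finally, a mixed model might seem to settle kits against recipes. It cannot: kits always come first and there is no recipe-only arm.

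**Conclusion.** The concern holds in a limited form. The plan names repeated measures ANOVA for food agency, diet quality, intuitive eating and stress, and has no rule for a missed assessment. If an Aim 2 or Aim 3 model spans all follow-ups in the classical form, the variance of a Phase 2 contrast is about 28% larger than with a mixed model at 10% independent loss ((0.293/0.259)² = 1.28) and about 68% larger at 20% ((0.349/0.269)² = 1.68, using expected information). With pairs from the end of fall, the excess is about 8% and 20% ((0.278/0.267)² and (0.315/0.288)²). Permanent dropout gives intermediate gains at Phase 2 and little at Phase 3. These sizes rest on assumed loss rates and a correlation of 0.5.

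The mismatch between the planned tests and Hypotheses 2a, 2b and 3 does not depend on missing data. The plan should be changed, but nothing here implies that the pilot cannot proceed or that a claimed power is missed, since none is claimed.

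**What to change.** 1. Reconcile the survey-timing statements, and state the time levels for each aim. If surveys really were taken only at baseline and study end, the phase-specific hypotheses could not be tested on them.
2. For each scale outcome, fit a linear mixed model to all observed assessments: class × support × phase, unstructured covariance with a named simpler fallback, and small-sample degrees of freedom. Keep the generalized linear mixed model for cooking frequency.
3. Report with intervals:
   - Class v control at the end of each phase, labelled non-randomised because controls were recruited separately (Consent Procedures, Control Condition).
   - Support v none at the ends of Phases 2 and 3, keeping the end-of-fall reference. Adjustment for pre-support scores is allowed for the randomised C v D comparison; at correlation 0.5 it gives variance 1 − 0.5² = 0.75, against 1.0 for a change score. Note that A v B was allocated by class period.
   - The Phase 2 v Phase 3 support difference, as descriptive only.
4. For stress, define who counts as receiving cooking support in each phase (A+B in Phase 1; state the rule for Phases 2 and 3), and report each follow-up separately.
5. Report numbers observed per group and phase. Add a missing-not-at-random sensitivity analysis, chiefly for Phase 3. For example, unobserved scores 0.25 to 0.5 SD worse in one arm with 20% to 40% missing move the contrast by 0.2 × 0.25 = 0.05 to 0.4 × 0.5 = 0.20 SD.

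The cost is SAP wording and slightly more analysis work. The model relies on data being missing at random. Over four occasions an unstructured covariance has 4 × 5/2 = 10 parameters for 64 students, hence the fallback. It does not cure separate control recruitment or allocation by class period.

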Hypothesis 3: Participants receiving cooking support will have lower scores on a measure of perceived stress than participants who do not receive cooking support. This will be true at all measurement time points.

Aim 4: To explore the reasons why students cook or do not cook.

Hypothesis 4: There will be common themes defining why student choose to cook or not cook at home.

Study Design: Describe the research design, including a description of any new methodology and its advantage over existing methodologies.

We propose a randomized trial to evaluate whether cooking classes produce greater gains in cooking skills and food agency compared to a control condition, as well as whether provision of meal delivery and recipes result in more frequent cooking than no meal delivery or recipe provision. We will randomize 64 students to either the intervention condition where they will take part in six weeks of hands on cooking classes, or the control condition where they will receive no cooking instruction during the fall semester. Following the completion of cooking classes and the start of the spring semester, one active cooking (treatment) group and one control group will receive another 12 weeks of intervention while the other two groups will receive no further instruction. The two continued intervention groups will be subscribed to a meal delivery service for six weeks, and then receive only recipes for another six weeks. Assessments will be conducted at baseline and following each phase of the intervention for all groups.

Study Population

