After the final cooking class, participants in groups B and D will receive no further instruction, though they will be asked to complete surveys and data collection through the remainder of the study phases. Phase 2 will begin in mid-January 2020. Participants in Groups A and C will receive weekly meal kit deliveries for 6 weeks. Meal kits will be delivered to students’ homes once per week and will include the ingredients and instructions for preparing 3 separate meals. Phase 3 will be immediately following phase 2. Participants in groups A and C will receive an email at the beginning of each week for the next six weeks that provides them with 5 healthy recipes developed by the study team. Students will generally receive the same recipes though; modifications may be made for participants with special dietary restrictions.

Facilities and Equipment Needed

Cooking Labs – The cooking classes and demonstrations will take place in the Nutrition and Food Sciences teaching kitchen located in the Marsh Life Science building. The teaching kitchen has room for 16 students to complete hands on cooking labs, and an additional space where students can get directions, eat, and watch cooking demos. The kitchens are fully stocked with the necessary kitchen equipment.

Follow-up Data Collection

Participants will be alerted by email to complete their follow-up assessment questionnaires which are anticipated to take approximately 30 minutes to complete and 3 days of the ASA24 (approximately 30 minutes per day).

All participants will be offered small incentives such as cooking equipment, cookbooks, gift cards, etc. (valued at approximately \$ 5-25) after completion of the follow-up data collection. Those in the Control Group will also receive a small incentive for completing their baseline measures.

For research involving survey, questionnaires, etc.: Describe the setting and the mode of administering the instrument and the provisions for maintaining privacy and confidentiality. Include the duration, intervals of administration, and overall length of participation. (describe and attach all instruments)

Not applicable

Questionnaires and ASA-24 logs will be administered at baseline and at the end of each study phase.

Photo elicitations and cooking frequency surveys will be administered weekly during the active study phases.

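### Aim 2 names only repeated measures ANOVA and does not say how the 12 weekly cooking counts of Phases 2 and 3 enter it, although Aim 1 gives the same outcome a mixed model

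*Combined protocol and SAP*

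**What the plan says.** In Statistical Considerations, the Aim 1 paragraph splits the outcomes by method. Intuitive eating, diet quality and food agency go to repeated measures ANOVA. For the weekly outcome, "A generalized linear mixed model design will be used to compare the frequency of cooking at home each week over time and between the groups".

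Under Aim 2, cooking frequency appears in both hypotheses. Hypothesis 2a reads "Meal delivery service will better maintain cooking frequency, intuitive eating skills, food agency and diet quality versus recipe provision only". Hypothesis 2b says that students who took the classes "will maintain higher levels of food agency, cooking frequency, and diet quality than those in the Control Condition". Two sentences of method follow:

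- Between subjects: "Repeated measures ANOVA analyses will be used to compare between subjects effects from the meal delivery and recipe only interventions", and the supported groups against control. This sentence names no outcome and no time points.
- Within subjects: the same method will "compare within subjects effects from end of fall semester to the end of each six-week material support intervention". This sentence gives time points but again no outcome.

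The mixed model is not mentioned under Aim 2.

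On data collection, the survey-administration section says "Photo elicitations and cooking frequency surveys will be administered weekly during the active study phases". The Study Design section fixes the length of follow-up: "The two continued intervention groups will be subscribed to a meal delivery service for six weeks, and then receive only recipes for another six weeks". The Intervention section keeps Groups B and D in data collection through the later phases. The Sample Size section gives about 64 students, set by kitchen capacity, and no power calculation.

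**The concern.** Aim 1 recognises that a weekly outcome needs a different model from the questionnaires and the diet score. Aim 2 uses the same weekly outcome and drops that distinction. An analyst following the Aim 2 paragraph has three ways to proceed:

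- take the weeks at the stated phase ends;
- enter all 12 weeks as levels of a repeated measures ANOVA;
- average the weeks within each phase.

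These differ in precision and in which students are kept, and nothing in the plan chooses between them. The Statistical Considerations section has no rule for missed weekly surveys. The choice could therefore be made after the data are seen.

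Aim 2 is where the question of maintaining gains is answered, and the pilot is meant to supply inputs for sizing a larger study. The variance it reports for cooking frequency will depend on which summary was used. Timing adds a smaller point. Phase 2 starts in mid-January 2020 and Phase 3 follows directly, so the last week of Phase 3 falls around mid-April 2020. The plan includes a questionnaire on changes to living situation and food access caused by COVID-19. A Phase 3 result resting on its final week alone could rest on an atypical week.

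**Working it through.** **The plan's own figure.** 4 groups × 16 = 64, which agrees with the plan. Each factor then compares 32 with 32: support (A and C against B and D) and classes (A and B against C and D). No power, effect size, SD or significance level is stated, so there is no planned power to reproduce.

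**Reading 1: end-of-phase weeks only.**

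- Weekly counts per student in Phases 2 and 3: 6 + 6 = 12. Planned total: 64 × 12 = 768.
- Used: 64 × 2 = 128. Unused: 768 − 128 = 640, or 640/768 = 83% (10 of 12 per student).

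Assumptions for power, none of them from the documents: two-sided 0.05, a difference of 0.5 weekly SD, the same correlation ρ between any two weeks, no missing weeks, clustering by class ignored, normal approximation.

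- SD of a k-week mean, with weekly SD = 1: √((1 + (k − 1)ρ)/k).
- Power = Φ(0.5/(SD × √(2/32)) − 1.96). Since √(2/32) = 0.25, this is Φ(2/SD − 1.96).
- Example, ρ = 0.3. Two weeks: SD = √(1.3/2) = 0.806, power = Φ(0.52) = 0.70. Twelve weeks: SD = √(4.3/12) = 0.599, power = Φ(1.38) = 0.92.

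| ρ | Two end weeks | All 12 weeks | Loss (points) | One end week | Six-week mean |
|---|---|---|---|---|---|
| 0.3 | 0.699 | 0.916 | 22 | 0.516 | 0.873 |
| 0.5 | 0.637 | 0.776 | 14 | 0.516 | 0.745 |
| 0.7 | 0.583 | 0.651 | 7 | 0.516 | 0.637 |
| 0.9 | 0.537 | 0.555 | 2 | 0.516 | 0.551 |

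The last two columns are for a comparison within a single phase.

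**Reading 2: all 12 weeks in a classical ANOVA.** A student with any missed week drops out. With an assumed non-response that is independent from week to week:

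- 5%: 0.95^12 = 0.540; 64 × 0.540 = 34.6, about 35 students.
- 10%: 0.90^12 = 0.282; 64 × 0.282 = 18.1, about 18 students.

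If missed weeks cluster in the same students, more complete series survive.

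**Reading 3: means of the available weeks.** Poisson counts were simulated with mean 3 a week, rate ratio 4/3, 32 per side and 2,000 runs per setting. A log-link comparison of student totals stood in for the mixed model; a generalized linear mixed model was not itself fitted.

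| Within-person correlation | Two end weeks | 12-week mean, normal theory | Log-link, all weeks |
|---|---|---|---|
| 0.3 | 0.56 | 0.78 | 0.78 |
| 0.5 | 0.37 | 0.46 | 0.48 |
| 0.7 | 0.23 | 0.26 | 0.30 |

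On one complete simulated dataset with normal outcomes, a linear mixed model and the between-subjects ANOVA test gave the same statistic, 2.88. Almost all of the loss therefore comes from which weeks are used and from missed weeks; the choice of ANOVA as such adds little.

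**The case against.** The strongest reply is that the plan can be read by measure: the mixed model for whatever is collected weekly, ANOVA for whatever is collected once per phase. The Aim 1 sentence is worded generally enough to cover all weeks, and the phase-end time points in Aim 2 suit the questionnaires and dietary recalls, which are taken at phase ends. This may well be the intention. But the sentence stands under Aim 1, Aim 2 does not refer back to it, and Aim 2 lists cooking frequency among the outcomes of the ANOVA paragraph.

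A second reply is that an ANOVA on phase means would lose little. That is correct, as the working shows, but the plan does not define such means. A third is that baseline compliance tasks and weekly reminders should keep non-response low, and that a pilot without a power target has no planned power to lose. Both points stand and limit the weight of the figures.

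A reader might go further than the documents allow in four ways:

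- That the weekly counts are discarded. The plan never says so; this follows only if the phase-end time points are applied to cooking frequency.
- That repeated measures ANOVA is itself the weak method. On complete data and the same weeks, it performs nearly as well.
- That both hypotheses suffer on their leading outcome. Cooking frequency is listed first in 2a, but food agency comes first in 2b.
- That Aim 1 and Aim 2 results could not be compared because of different scales. The plan states no distribution or link, and adjusted weekly means can be reported from either analysis.

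**Conclusion.** The gap is real, and its cost is conditional. The same weekly outcome has a mixed model in Aim 1 and only repeated measures ANOVA in Aim 2, with no statement of how 12 weekly counts enter. On the end-of-phase reading, 83% of the planned Phase 2 and 3 counts are unused, and power falls by about 22 points at a week-to-week correlation of 0.3 and about 2 at 0.9. On the all-weeks classical reading, the cost is students: about 35 or 18 of 64 remain at 5% or 10% weekly non-response. On the phase-mean reading the cost is small. The effect size, correlation and non-response rates are assumptions, and clustering by class is ignored. The Aim 2 paragraph should be changed because the plan already contains a suitable method for this variable and the change needs no new data. The trial's conclusions are not shown to be invalid.

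**What to change.** In the Aim 2 paragraph, state that weekly cooking frequency is analysed with the Aim 1 generalized linear mixed model, extended to every available weekly survey of Phases 1 to 3. Specify a student random intercept; terms for phase, class and support; and phase-by-class and phase-by-support interactions. Name the distribution and link, which Aim 1 also leaves open, and report adjusted weekly means by group and phase so that Phases 1, 2 and 3 can be read together. Limit repeated measures ANOVA to the outcomes measured once per phase.

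If the sponsor prefers to keep ANOVA for this outcome, the plan should at least define the phase summary and how missed weeks are handled.

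The cost is a sentence or two in the analysis section and slightly more modelling work. Students with some missed weeks stay in the analysis.

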With the rise in obesity in America correlating strongly with the decline in the frequency that Americans cook at home, cooking may be an important behavior to encourage to promote health. Increasing the prevalence of Americans who cook meals at home may be an important health behavior to target, because cooking at home is widely regarded as being healthier than consuming food away from home. While interventions are limited in number and scope, the positive benefits of cooking at home on dietary quality seem to cut across age groups and populations from college students to older adults.^{6,7} Cooking classes may be an important intervention target because they may increase one’s food agency. Thinking of cooking as a health behavior, cooking classes may be equivalent to exercise classes for someone trying to increase their physical activity. The exercise classes give one the skills, social structure, and self-efficacy to begin exercising on one’s own. This study is designed to test whether cooking classes could do the same for someone’s food agency and cooking frequency.

The proposed pilot study is a trial to evaluate whether cooking classes produce greater gains in cooking skills and food agency compared to a control condition that does not receive cooking classes, as well as whether provision of meal delivery and recipes result in more frequent cooking than no meal delivery or recipes. There will be three phases to the study intervention and four study conditions. All conditions will receive 6 weeks of cooking classes, either active or demonstration, and two conditions will also receive a continued intervention including 6 weeks of meal kit delivery service followed by another 6 weeks of recipe provision.

Phase 1- Cooking classes or control condition. All participants in the cooking classes condition will attend 1 kitchen intensive session followed by 1 cooking class per week for 6 weeks. Control condition participants will receive no cooking instruction.

Phase 2- Meal Kits. Assigned participants will receive meal kit deliveries once per week for 6 weeks.

Phase 3- Recipes. Assigned participants will receive 5 healthy recipes by email once per week for 6 weeks.

We will randomize 64 students to one of four intervention conditions.

Group A (n=16) - Active cooking classes followed by meal kits and recipes

Group B (n=16) - Active cooking classes followed by no further instruction

Group C (n=16) – Control condition followed by meal kits and recipes

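### The Aim 2 analysis plans a between-subjects comparison of kits with recipes that the design does not contain, and names its comparator for support by a term that elsewhere covers a supported group

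*Combined protocol and SAP*

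**What the plan says.** Under Statistical Considerations, Aim 2, repeated measures ANOVA is to "compare between subjects effects from the meal delivery and recipe only interventions". The same sentence goes on to plan a second comparison: "as well as to compare the material support interventions against the control group". The next sentence adds repeated measures ANOVA to "compare within subjects effects from end of fall semester to the end of each six-week material support intervention". Neither sentence lists group letters. Hypothesis 2a predicts that kits will maintain outcomes better than recipes alone, and that both will do better than no cooking support.

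The opening summary defines four groups of 16: A (classes, then kits and recipes), B (classes only), C (control, then kits and recipes) and D (control only). Study Design says that "one active cooking (treatment) group and one control group will receive another 12 weeks of intervention", and that these two groups will be "subscribed to a meal delivery service for six weeks, and then receive only recipes for another six weeks". The section on Phase 2 and Phase 3 support and the Intervention section agree.

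The summary defines the Control Condition as not attending the weekly classes. Follow-up Data Collection says: "Those in the Control Group will also receive a small incentive for completing their baseline measures". Baseline comes before any support, so that use covers C and D together. The summary frames the support question differently, as whether "provision of meal delivery and recipes result in more frequent cooking than no meal delivery or recipes". Study Design repeats it as whether "provision of meal delivery and recipes result in more frequent cooking than no meal delivery or recipe provision".

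**The concern.** Hypothesis 2a makes two claims, and the analysis text fits neither.

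The claim that kits do better than recipes is assigned to a comparison between different people. The design has no two sets of people who differ in that way.

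The claim that support does better than no support is assigned to a comparator whose name, as used elsewhere, includes a group that gets the support. Taken literally, this mixes the support effect with the class effect. The class effect is also the less secure of the two, because the documents conflict on how students reach the class or control condition. The summary and Study Design say 64 students are randomised. Procedures places students in class periods by availability or recruits them as controls, and Consent Procedures draws controls from applicants who did not go on with recruitment.

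Sample Size says the pilot data will be used to size a larger study, so a mixed or undefined contrast would carry forward. Leaving the groups unnamed also allows the comparator to be chosen after the results are known.

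**Working it through.** **1. The plan's own figure.** 4 groups × 16 = 64, which matches the stated total. There is no power calculation to reproduce.

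**2. Who receives what** (summary, Study Design, Intervention).

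| Group | n | Classes | Phase 2 | Phase 3 |
|---|---|---|---|---|
| A | 16 | yes | kits | recipes |
| B | 16 | yes | none | none |
| C | 16 | no | kits | recipes |
| D | 16 | no | none | none |

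In Phase 2, 32 students have kits and 0 have recipes as their support. In Phase 3, 0 have kits and 32 have recipes. The number given recipes without earlier kits is 0. In neither phase is there anyone on the other side of a between-subjects comparison of kits with recipes.

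**3. What each comparator estimates.** Let s be the support effect, and c1 and c2 the class effect at end of fall and in spring. Take equal groups and additive effects.

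- Spring levels: A = c2 + s, B = c2, C = s, D = 0.
- A+C v C+D: (s + c2/2) − s/2 = s/2 + c2/2. Group C cancels, leaving half of A minus D.
- A+C v B+D: (s + c2/2) − c2/2 = s.
- Change from end of fall: A = c2 + s − c1, B = c2 − c1, C = s, D = 0.
- A+C v C+D on change: s/2 + (c2 − c1)/2.
- A+C v B+D on change: s.

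No effect size has to be assumed. If classes and support interact, A+C v B+D is the average of A v B and C v D.

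**4. What the data can say about kits versus recipes.** Let k be the effect of kits, r the effect of recipes after kits, and t the calendar change from Phase 2 to Phase 3.

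- Change within A+C: (r − k) + t.
- Change within B+D: t.
- Net change: r − k, if t is the same in both sets. If t differs, the net is (r − k) + (t in supported − t in unsupported).

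Calendar change is a real possibility. Phase 2 starts in mid-January 2020. Taking 15 January as an assumption, 42 days later is 26 February and 84 days later is 8 April, so Phase 3 falls between those dates. The plan adds a questionnaire on changes in living situation and food access due to COVID-19.

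**5. Precision cost of netting.** In SD units, with between-phase correlation ρ (not given in the documents, so a range is shown), 32 students per side, and no allowance for clustering or dropout:

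- Uncontrolled change in A+C: √(2(1−ρ)/32).
- Net of B+D: √(2(1−ρ)) × √(2/32).

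| ρ | Uncontrolled SE | Net SE |
|---|---|---|
| 0.3 | 0.209 | 0.296 |
| 0.5 | 0.177 | 0.250 |
| 0.7 | 0.137 | 0.194 |

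The ratio is √2 throughout.

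**The case against.** On the comparator, the surrounding text largely answers the question. Hypothesis 2a stands just above the analysis sentence and sets support against no cooking support. The summary and Study Design do the same. Sample Size speaks of two intervention and two control groups for each study phase, which fits B and D as the controls in Phases 2 and 3. This objection stands. A reader might infer that the investigators would run A+C against C+D, or use D alone as the only control group without support. No section proposes either analysis. What remains is a label that conflicts with its use elsewhere.

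On kits versus recipes, the first half of the sentence could mean the between-group effect of each support in its own phase. That reading is strained, because the second half already compares support with control. The following sentence does plan within-person changes to the end of each support phase, and a Phase 2 to Phase 3 change could be derived from them. It names no kits-versus-recipes contrast, however. A reader might also infer that B and D would be left out of any such change. The documents do not say so: B and D complete data collection through all remaining phases.

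Finally, this is a pilot without a power calculation. That limits how serious the point is, but it does not supply the missing comparison.

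**Conclusion.** The kits-versus-recipes comparison is wrong as written. It has no participants, and that part of Hypothesis 2a can be addressed only by change within A and C. This follows directly from the allocation table and rests on no assumed value.

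The comparator is a conflicting label and not a demonstrated wrong analysis. If the label were applied literally to C+D, the result would be half the support effect plus half the class effect, where A+C v B+D gives the support effect alone. Those weights assume equal groups and additive effects.

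Netting against B and D gives r − k only if calendar or COVID-19 change is the same in supported and unsupported students. Disruption that altered how well recipes work would not be removed. The standard errors are illustrative: the documents give no SD or correlation, and support is assigned by class period in the class groups, which these figures ignore.

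The sentence should be corrected before analysis. The data to be collected are not in question.

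**What to change.** Replace the Aim 2 analysis sentence with contrasts named by group.

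- **Support (Hypothesis 2a):** A+C versus B+D with class in the model, reported separately at Phase 2 (kits) and Phase 3 (recipes after kits). Report A versus B, which is the maintenance question in Aim 2, and C versus D, each with confidence intervals.
- **Model:** a Phase 2 and 3 repeated measures model with class, support, phase and all their interactions, adjusted for the end-of-fall value. The full set of interactions is needed so that A versus B and C versus D can be estimated freely at each phase. Use the corresponding generalized linear mixed model for weekly cooking frequency, which the plan names only under Aim 1.
- **Kits versus recipes:** the Phase 2 to Phase 3 change within A and C, net of the same change in B and D. State that the order is fixed, that carry-over from kits cannot be separated, and that netting relies on equal calendar change in supported and unsupported students.
- **Hypothesis 2b:** A+B versus C+D on Phase 2 and 3 levels, without the end-of-fall adjustment because that value is measured after the classes. Note beside it that Procedures and Consent Procedures describe class placement by availability and separate recruitment of controls, in conflict with the randomisation stated in the summary and Study Design.

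The cost is rewording and a little extra analysis, with no change to data or participants. The netted kits-versus-recipes estimate has a standard error √2 times that of the uncontrolled change. The change does not deal with the assignment of support by class period, which needs its own handling.
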